3.2.3 SECONDARY: Technical Success

Technical assessment data will include:

- Taste of the PE solution
- Taste of the PRV111 patch
- Adhesion, including the time of adhesion of PRV111 patch
- PRV111 patch peel-off
- Residual cisplatin level in the patch after the application period. All PRV111 patches will be assessed for the amount of residual cisplatin in each patch after each application period. If the product detaches prematurely, the residual cisplatin will be assessed and the time of detachment will be noted.

Results will be summarized using descriptive statistics.

4 Safety Assessments

Safety observations and measurements including study drug exposure, AEs, laboratory data, physical examination findings, VS, weight, and concomitant therapy will be summarized and presented in tables and listings. SAEs will be collected within 30 days post-surgery. Certain key parameters such as “Expected” and “Related to treatment” will be recorded. AEs that occur from visit 1 to visit 5 are documented. AEs (not SAEs) during or after surgery are not documented since the oral tumor and reconstructive surgeries can result in many AEs. The list of expected SAEs due to oral cancer surgery and reconstructive surgery is included in the Investigator Brochure. Laboratory parameters will be summarized using descriptive statistics and data listings. The incidence of clinically significant abnormalities will be summarized. Physical examinations, VS, and weight will be summarized by changes from baseline values using descriptive statistics.

AEs occurring after the start of treatment are TEAEs. The severity of the TEAEs will be graded according to the CTCAE criteria, version 4.0. The severity of oral mucositis will be graded according to the WHO grade. The number and percentages of subjects experiencing TEAEs will be tabulated by system organ class and preferred term. Assessments of TEAEs will include characterization of the type, incidence, severity, seriousness, and relationship to treatment. Summary subject listings will be provided for subjects with dose modification, SAEs, TEAEs resulting in study discontinuation, and deaths. The rates of local tolerability and oral mucositis will be reported.

Safety assessments include:

- Physical Examination, Vital Signs, Weight
- Oral Cavity Examination
- Neck Lymph Nodes Examination
- Safety Laboratory Assessments
- Electrocardiograms
- Adverse events

4.1 *Physical Examination, Vital Signs, Weight*

A complete physical examination will be performed by the Investigator or Sub-investigator.

The physical examination will include a review of all body systems (head, eyes, nose and throat, cardiovascular, respiratory, gastrointestinal, musculoskeletal, neurological, lymph nodes, dermatological, extremities/joints), and weight.

[figure not shown]
Seated blood pressure (mmHg), pulse (beats per minute) and temperature (degrees Celsius) will be measured after the subject has been sitting for at least 3 minutes.

Neuropathy and ototoxicity will be assessed via clinical examination since cisplatin can potentially cause neurotoxicity and ototoxicity. Questions will be asked to document symptoms such as tinnitus, pain in the extremities, or loss of sensation in the eCRFs.

4.1.1 Physical Examinations Analysis:

A complete general physical examination, including height and weight and vital signs (VS), will be assessed and recorded. Seated blood pressure (mmHg), pulse (beats per minute) and temperature (degrees Celsius) will be measured after the subject has been sitting for at least 3 minutes. Measured values of all vital signs and the corresponding CFBs (Change from baseline) will be summarized with descriptive statistics by visit. All observed vital signs and corresponding CFB will be presented in a listing. All abnormal physical examination findings will be included in the adverse events listings and summary tables.

Height is measured only at the screening visit and will not be included in the vital signs summary table but will be included in the listing.

4.2 *Oral Cavity Examination*

[figure not shown]
A systematic and thorough visual and manual oral examination will be performed. This will include a visual examination of all the soft tissues of the mouth, including manual extension of

the tongue to examine its base, a bi-manual palpation of the floor of the mouth, and a digital examination of the borders of the tongue.

Special attention must be given to the application site and the tumor, with documentation of any local adverse reactions, including documentation with photographs if warranted.

4.2.1 Oral Cavity Examination Analysis:

A systematic and thorough visual and manual oral examination will be performed. This will include a visual examination of all the soft tissues of the mouth, including manual extension of the tongue to examine its base, a bi-manual palpation of the floor of the mouth, and a digital examination of the borders of the tongue. Results will be summarized using descriptive statistics

[figure not shown]

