#### Figure 5. Stage 2b safety and efficacy scheme

*Note:* The surgery is to be performed no later than 42 days post Visit 1.

All subjects will subsequently undergo standard of care, surgical ablation of the tumor and satellite nodes, and possibly additional radiotherapy and chemotherapy. All subjects will be followed for up to 6 months post-surgery at 3 visits: 1 month, 3 months, and 6 months post-surgery for loco-regional response and safety. Follow-up visits may coincide with standard of care follow-up visits, if deemed appropriate by the Principal Investigator.

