#### 9.6.8 Post-Treatment Follow-Up (Visits 7, 8, & 9)

All subjects will be followed for up to 6 months post-surgery at 3 visits: 1, 3, and 6 months postsurgery for loco-regional response and safety. Follow-up visits may coincide with standard of care follow-up visits, if deemed appropriate by the Principal Investigator.

- Perform and record results of physical examination and VS
- Perform visual oral examination and neck lymph node examination to assess for signs of loco-regional recurrence
- Review any concomitant therapy

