- c VS: seated blood pressure and pulse will be measured after the subject has been sitting for at least 3 minutes, respiration, temperature, height and weight will be recorded at every visit. VS will be obtained pre-dose at all visits and subject will also be monitored at 30+5 minutes, 60+5 minutes and 120+5 minutes following application of the last patch applied at Visits 1 and 4 and at 30+5 minutes post last patch application at Visits 2 and 3.
- d Take photos of the tumor region for further assessment of tumor shrinkage.
- e Every attempt should be made to use the same test for each subject for both timepoints.
- f CBC and chemistry panel (creatinine to determine the creatinine clearance, BUN, LFT, electrolytes (potassium, magnesium, calcium, and sodium), urinalysis.
- g Tissue will be collected at Screening but the HPV status will be ascertained at any time during the study using immunohistochemistry for p16 according to institutional clinical protocols.
- h Serum pregnancy test to establish eligibility for female subjects of childbearing potential. A negative urine pregnancy test must be documented within 7 days prior to the first treatment visit, and at Visit 5.
- i Visit 1 & 4: PK blood samples for total platinum collected pre- treatment (time -15 to 0 minutes), and 30±5 minutes, 60±5 minutes and 120±5 minutes post removal of last patch.
- j Visit 2 & 3: PK blood samples for total platinum collected pre- treatment (time -15 to 0 minutes), and 30±5 minutes, post removal of last patch and PE application.
- k Sampling for tumor and lymph nodes (if available) platinum levels.

- l Photos need to be taken prior to patch application.
- m Confirmation of tumor histology by a clinical pathologist is required prior to enrollment. A final pathology report, issued by a clinical pathologist is required following surgical resection of the tumor specimen.
- n Taste of the PE solution and patch, adhesion, peel-off, residual cisplatin level in the patch.
- o Performed after surgery if possible
- p PE should be applied to the tumor area prior to first patch and allow to stay for 5 minutes. Then applied again to the tumor area for 1 minute. Note that the mouth should be kept open for the saliva not wash off the PE.
- q Use "0.05" cm for the "Height" of a flat tumor. If a concave tumor, the "Height" can be shown as a negative number. If a non-measurable dent, use "-0.05" cm.
- r Only SAEs within 30 days post visit 5 need to be recorded.

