An AE (also known as an “adverse experience”) is defined as any untoward medical occurrence associated with the use of a drug in humans, whether or not considered drug related (US Code of Federal Regulations [CFR] 312.32).

An AE can therefore be any unfavorable and unintended sign (including an abnormal laboratory finding), symptom, or disease temporally associated with the use of the drug, without any judgment about causality. A TEAE, treatment emergent adverse event is an AE that occurred on or after the start of treatment.

All clinical AEs noted during the study will be reported on the appropriate AE page of the CRF.

AEs that are serious, unexpected, and at least possibly related to study participation will be reported to the IRB and to the US FDA within the timelines described below. All other AEs, such as those that are expected, or definitely not related to the study participation, are to be reported per the IRB's policy and to FDA as part of regular data submission at the time of annual Investigational New Drug report.

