4.6.9 Recording Adverse Events

All AEs (including SAEs) within the 5 pre-surgery visits are to be accurately recorded on the AE/SAE page(s) of the CRF. In addition, any SAEs within 30 days of visit 5 will need to be recorded. The Investigator will carefully evaluate each AE to determine:

- Duration (start and end dates)
- Severity (grade)
- Seriousness
- Relationship to study drug (Not Related, Possible, Definite)
- Action taken (none, study drug modification, medical intervention)
- Outcome (resolved without sequelae, resolved with sequelae, ongoing)

The Investigator will evaluate all AEs and SAEs with regard to maximum intensity and relationship to study drug. Maximum intensity should be assigned using one of the severity grades as outlined in the NCI CTCAE v4.0. If the AE is not specifically listed in CTCAE v4.0, the following grades will be used:

- Grade 1: mild
- Grade 2: moderate
- Grade 3: severe
- Grade 4: life-threatening or disabling
- Grade 5: death

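### SAP 4.1.1 sends every abnormal physical examination finding to the adverse event tables, which conflicts with the pre-surgery AE window stated elsewhere and sets no new-or-worse condition

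*SAP*

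**What the plan says.** The analysis rule for physical examinations, in SAP 4.1.1, is: "All abnormal physical examination findings will be included in the adverse events listings and summary tables". It carries no visit range, no test of clinical significance and no comparison with baseline.

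Examinations continue after surgery. For Visits 7, 8 and 9, at 1, 3 and 6 months, Protocol 9.6.8 lists: "Perform and record results of physical examination and VS". By then, according to Protocol 6.1, subjects have had "surgical ablation of the tumor and satellite nodes, and possibly additional radiotherapy and chemotherapy".

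SAP 4.6 defines treatment emergence by its start only: "A TEAE, treatment emergent adverse event is an AE that occurred on or after the start of treatment".

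Other places set a window. SAP 4 states: "AEs that occur from visit 1 to visit 5 are documented". It adds: "AEs (not SAEs) during or after surgery are not documented since the oral tumor and reconstructive surgeries can result in many AEs". SAP 4.6.9 gives the recording rule: "All AEs (including SAEs) within the 5 pre-surgery visits are to be accurately recorded on the AE/SAE page(s) of the CRF". Protocol 9.3.6.6 has the same rule. Footnote r to the schedule of events, on the Visit 5 AE assessment, reads: "Only SAEs within 30 days post visit 5 need to be recorded". The statistical methods in the protocol synopsis describe the AE incidence summary as one of events before surgery.

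**The concern.** SAP 4.1.1 takes examination data into the AE tables without the limits that every other section applies. Two kinds of finding could enter by that route:

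- **Post-surgical findings at Visits 7 to 9.** The examination covers the head, nose and throat, and lymph nodes, so it reaches the operated region. Consequences of resection, node removal or adjuvant treatment would be abnormal findings dated after the start of PRV111.
- **Abnormalities already present at baseline** and written down again at Visits 2 to 5. These visits lie inside the AE window, so the window cannot screen them out.

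The trial has one arm. The treatment-emergent tables carry the descriptive safety account, and no comparator shows how much of the incidence is background. If 4.1.1 is followed, the content of those tables depends partly on how each examiner writes up an expected post-operative examination. Two programmers working from the same SAP could also produce different tables from the same data, one following 4.1.1 and the other SAP 4.

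**Working it through.** The plan states no figure to reproduce here. The check sets the passages side by side and counts visits.

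**1. Examinations and AE assessments in the schedule of events**

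| Visits | Physical examinations | AE assessment scheduled |
|---|---|---|
| Screening and Visit 1 (pre-dose) | 2 | yes |
| Visits 2 to 5 | 4 | yes |
| Visits 7 to 9 | 3 | no |
| Total | 2 + 4 + 3 = 9 | |

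The 4.1.1 rule therefore conflicts with the AE window at 3 of 9 scheduled examinations.

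**2. What each rule does with a non-serious abnormal finding**

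| Finding | SAP 4.1.1 with SAP 4.6 | SAP 4, SAP 4.6.9, Protocol 9.3.6.6, footnote r, synopsis |
|---|---|---|
| New at Visits 2 to 5 | in AE tables, treatment-emergent | in AE tables |
| Present at baseline, unchanged at Visits 2 to 5 | in AE tables; treatment-emergent only if dated from the visit and not from its true onset | no explicit new-or-worse rule |
| Visits 7 to 9 | in AE tables, treatment-emergent | not documented as an AE |

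**3. Does any text say which rule prevails?** None does. The window passages govern what is documented or recorded. SAP 4.1.1 is an analysis instruction, and it is the only rule that would carry non-serious findings from Visits 7 to 9 into the tables. SAP 4 and Protocol 10.5.6 both also plan to summarize physical examinations as changes from baseline, and neither sends all findings to the AE tables. SAP 7 states that no departure from the protocol is planned.

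**4. Denominator.** SAP 5.3 uses the Safety Population for safety summaries, meaning every subject with at least one patch applied (SAP 5.3.1). Enrolment can reach 10 + 21 = 31, so the Safety Population can hold up to 31 subjects. The 11 evaluable subjects are the efficacy target and not the safety denominator. The documents give no frequency of abnormal findings, so no incidence can be computed.

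**5. Dose decisions.** Protocol 8.4 ends the DLT period 14 days after the last treatment application or at surgery, whichever comes first. Visits 7 to 9 fall after that in every case.

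**6. The two SAE windows.** SAP 4 collects SAEs to 30 days after surgery. SAP 4.6.9, Protocol 9.3.6.6 and footnote r use 30 days from Visit 5. At the minimum intervals, Visit 4 falls 3 × 48 hours = 6 days after Visit 1, and Visit 5 falls 72 hours = 3 days later, on day 6 + 3 = 9. Surgery may take place up to 42 days after Visit 1, which is 42 − 9 = 33 days after such a Visit 5. At that extreme the window counted from Visit 5 closes before surgery, so the two rules can differ materially.

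**The case against.** The strongest reply is that the plan already excludes what is feared. SAP 4 is the parent section of 4.1.1, and it leaves out non-serious events during and after surgery for the very reason that surgery produces many of them. Four other places agree. With no AE assessment at Visits 7 to 9, a post-operative finding would have no planned record of grade or relationship. This stands as evidence of the sponsor's intent. It is also why a reader should not infer that surgical sequelae *are* counted as events of PRV111. The supportable statement is that they *would* enter if 4.1.1 were applied as written. The reply does not remove the contradiction, because nothing subordinates 4.1.1 to the window.

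On baseline findings, SAP 4.6 requires the event to have occurred on or after the start of treatment, and SAP 4.7 has a separate table of AEs before treatment. This handles them in part, provided each finding carries its true onset date. SAP 4.1.1 does not say that it will.

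The visible lesion and the resection defect belong mainly to the oral cavity examination, which SAP 4.2.1 analyses separately, as SAP 4.3.1 does for neck nodes. This stands, and it weakens any argument that the baseline tumor alone fills the table. Lymph nodes and throat remain among the systems listed for the general examination.

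SAP 4.7 also tabulates events by relationship, so a treatment-emergent event is not automatically attributed to PRV111. That is correct, but the table of all treatment-emergent events is not split, and relationship may be missing for findings made at visits without an AE assessment.

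**Conclusion.** The point holds as an internal contradiction with a practical consequence. SAP 4.1.1 conflicts with the stated AE window at 3 of 9 examinations, lacks a new-or-worse condition, and relies on a treatment-emergent definition without an end. Applied as written, it would add post-surgical findings, and possibly pre-existing ones, to the treatment-emergent tables of the Safety Population.

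The number of events or subjects affected cannot be derived from the documents. A reader might infer that almost every subject, for instance 11 of 11, would show a head-and-neck event whatever PRV111 does. The documents do not support that figure: it uses the evaluable target as the safety denominator, and it is a worst case that sets aside every passage limiting AEs to the pre-surgery visits. Nor does the point touch dose selection or the tolerability criterion, which rest on DLTs within a period that ends no later than surgery.

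The conclusion assumes only that a programmer could follow 4.1.1 literally. It should be corrected before the safety tables are programmed.

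**What to change.** Replace the 4.1.1 sentence with wording such as: *Non-serious physical examination findings are included in the TEAE tables only if new or worse than at Visit 1 pre-dose and with onset up to Visit 5, consistent with Sections 4 and 4.6.9. Findings at Visits 7 to 9 are shown in a separate physical examination listing. Findings that meet the SAE definition follow the SAE collection window.*

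Then:

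- Give the non-serious treatment-emergent tables in SAP 4.7 the same end date. A cut-off at surgery would not match the documented window, which ends at Visit 5. A cut-off without the exception for serious findings would drop post-surgical SAEs that the SAP collects and tabulates.
- Reconcile the two SAE windows, 30 days after Visit 5 and 30 days after surgery, across SAP 4, SAP 4.6.9, footnote r and Protocol 9.3.6.6.
- Confine the new wording to the TEAE tables. Visit 5 may take place 72 hours after the last treatment, while the DLT period can run to 14 days after the last application, so DLT counting should stay on its own period.

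The cost is a few sentences of SAP text, alignment of the protocol's SAE window if that is the one changed, and one programming condition on dates and baseline status. The tables themselves need no new data. The small downside is that non-serious post-surgical findings appear only in a listing.

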4.3 Neck Lymph Nodes Examination

A cervical and local lymph nodes examination will be performed.

4.3.1 Neck Lymph Nodes Analysis

A cervical and local lymph nodes' examination will be performed. Results will be summarized using descriptive statistics.

4.4 Safety Laboratory Assessments

Clinical laboratories to be assessed will be as in [Table 3](#).

[figure not shown]
Table 3. Clinical Laboratories

COMPLETE BLOOD COUNT	CHEMISTRY PANEL	

 • hematocrit • hemoglobin • platelet count • red blood cell count • white blood cell count and differential (absolute and percentage); neutrophils, lymphocytes, monocytes, eosinophils, basophils, and reticulocyte count 	
 • alanine aminotransferase • albumin • alkaline phosphatase • aspartate aminotransferase • bilirubin (direct and total) • blood urea nitrogen • calcium • CO₂ 	
 • chloride • creatinine^a • gamma glutamyl transferase • glucose • magnesium • potassium • sodium • total protein
URINALYSIS		

 • urinalysis dipstick with reflex microscopic examination for abnormalities 		

^a Creatinine Clearance will be used to assess renal function using Cockcroft-Gault Equation

4.4.1 Laboratory Tests Analysis:

Laboratory values such as routine blood chemistry, hematology, and urinalysis will be measured for each subject. Summary statistics will be provided by visit for blood chemistry and hematology and the corresponding CFBs. The calculation for CFB is described in Section 9.5. If the value at Baseline is missing, then CFB will be defined as the change from the value recorded at Screening. Urinalysis results and serum and urine pregnancy test results will be included in the listings of laboratory parameters but not in the summary tables. Laboratory ranges displayed and used for normal values will be per site. If a laboratory is missing ranges, the next most-similar lab will be used. For example, if Site 001 is missing a normal range, another lab from the same site will be used as reference (i.e. Baylor HHS is missing red blood cells, the value from Baylor Austin will be used). Data will be displayed per lab and per patient.

[figure not shown]

4.5 *Electrocardiograms*

Electrocardiograms (ECGs) will be evaluated for clinically relevant changes from Baseline.

4.5.1 ECG Parameters Analysis:

ECG parameters will be reported as normal or abnormal per subject and per visit.

4.6 *Adverse Event Definitions/Reporting Requirements*

An AE (also known as an “adverse experience”) is defined as any untoward medical occurrence associated with the use of a drug in humans, whether or not considered drug related (US Code of Federal Regulations [CFR] 312.32).

An AE can therefore be any unfavorable and unintended sign (including an abnormal laboratory finding), symptom, or disease temporally associated with the use of the drug, without any judgment about causality. A TEAE, treatment emergent adverse event is an AE that occurred on or after the start of treatment.

All clinical AEs noted during the study will be reported on the appropriate AE page of the CRF.

AEs that are serious, unexpected, and at least possibly related to study participation will be reported to the IRB and to the US FDA within the timelines described below. All other AEs, such as those that are expected, or definitely not related to the study participation, are to be reported per the IRB's policy and to FDA as part of regular data submission at the time of annual Investigational New Drug report.

4.6.1 Expected Events

Expected events are those that have been previously identified as resulting from administration of the study drug. An AE is considered unexpected, for expedited reporting purposes only, when either the type of event or the severity of the event is not listed in the current Investigator's Brochure (IB).

4.6.2 Suspected Adverse Reaction

A suspected adverse reaction is a subset of all AEs for which there is a reasonable possibility (ie, evidence to suggest a causal relationship between the drug and the AE) that the drug caused the event. Suspected adverse reaction implies a lesser degree of certainty about causality than adverse reaction.

